12.1. Endpoints

The primary, secondary, and tertiary endpoints of the trial are listed in Table 2 below and described in detail in the following paragraphs. In addition to these endpoints, several ancillary studies will be conducted to maximize the scientific knowledge gained regarding the neurobiological and physiological effects of exercise in patients with MS (see section 12.2.).

Endpoint	Construct	Measure
Primary endpoint	Verbal Learning and Memory	VLMT
Secondary endpoints	Functional connectivity	rs MEG, rs fMRI
	Structural integrity and connectivity	GM density, DTI
	Other cognitive functions	Neuropsych. battery
Tertiary endpoints	Walking ability	6MWT, accelerometry
	Motor coordination and balance	MFT-S3
	Well-being and quality of life	Patient-reported outcomes

Table 2. Overview of primary, secondary, and tertiary endpoints of the AERCONN trial.

12.1.1. Primary endpoint:

The primary endpoint of this study will be the Verbal Learning and Memory Scale (VLMT, Helmstaedter, Lendt and Lux, 2001) after 3 months of training. Learning and

memory are important domains of cognitive function and frequently impaired in MS, with important implications for quality of life, vocational status and psychosocial problems (Chiaravalotti and De Luca, 2008; Langdon, 2011). Moreover, MS patients rank memory and thinking amongst the most important body functions (Heesen et al., Mult Scler 2008).

Learning and memory is among the cognitive domains most consistently shown to improve after aerobic exercise training in numerous studies including patients with chronic diseases and aged healthy individuals (Smith et al., Psychosom Med 2010). Moreover, in our previous pilot trial of aerobic exercise in progressive MS (Briken et al., MSJ 2013), verbal learning and memory as measured by the VLMT was significantly increased after the training program.

12.1.2. Secondary endpoints:

Secondary endpoints include imaging-based measures of brain integrity and connectivity as well as neuropsychological tests covering several domains of higher-order brain function.

Functional connectivity will be assessed using resting-state MEG and fMRI analyses. It will be compared between patients and healthy controls both on sensor and source level. As measures we use quantities, which are robust to artifacts of volume conduction, specifically the imaginary part of coherency, power correlations corrected for mixing artifacts, and, on source level, multivariate measures, which optimize source orientation to detect neural interactions. Although the approach is exploratory we will specifically concentrate on motor systems and working memory and relate results to findings from structural connectivity analysis.

Structural connectivity will be evaluated by measuring the fractional anisotropy (FA) calculated from Diffusion-Tensor Imaging data (DTI). Overall cortical es well as regional (i.e. corpus callosum, primary and secondary motor cortex) FA values will be obtained. In addition, connectivity will be analyzed by probabilistic tractography focusing on the motor system as well as brain areas involved in processing speed and working memory as the core neuropsychological deficit in MS and correlated with neuropsycological parameters as well as functional connectivity measures.

Structural integrity of gray matter will be assessed by gray matter density measurement on T1 weighted MR images. Here, we will obtain overall and focal (cortex, hippocampus, thalamus) gray matter density measures

In addition to imaging makers of brain structure and connectivity, we will analyze several domains of *higher-order brain function* as secondary endpoints. These include attention (Test of Attentional Performance, TAP), visuospatial learning and memory (Brief Visuospatial Memory Test Revised, BVMT-R, Benedict et al. 1997), processing speed (Symbol Digit Modalities Test, SDMT, Smith 1973, Paced Auditory Serial Addition Task, PASAT, Gronwall, 1977), working memory (Corsi Block, Corsi 1972), and social cognition (theory of mind as determined by the Movie for Assessment of Social Cognition, Dziobek et al., 2006). Cognitive function is of major clinical importance in MS since is linked to quality of life and vocational status. In addition, currently available disease-modifying therapies have limited effects on cognition and attempts to develop pharmacological therapies for cognitive impairment have been unsuccessful in MS (Benedict & Zivadinov Nat Rev Neurol 2011). Therefore, exploring novel treatment options for cognitive dysfunction in MS such as exercise is highly relevant for MS care.

12.1.3. Tertiary endpoints:

Tertiary outcomes include objective measures of *walking ability*. We will obtain total distance (in meters) during the six-minute walk test (6MWT) as well as "real-life" walking speed as measured by the Actibelt® over the course of 7 days.

Furthermore, we will obtain patient-reported outcome measures (PRO) to assess subjective well-being and quality of life. These measures include the Inventory of Depressive Symptoms (IDS-30SR), the Fatigue Scale for Motor and Cognitive Function (FSMC, Penner et al., 2009), the Hamburg Quality of Life Questionnaire for Multiple Sclerosis (HAQUAMS, Gold et al., 2001), and the Multiple Sclerosis Walking Scale-12 (MSWS-12, Hobart et al.)

Finally, we will objectively assess motor coordination and balance using the MFT-S3.

12.2. Ancillary studies:

In order to maximize the scientific insight that can be gained from this phase IIa trial with respect to the neurobiology and physiology of exercise in multiple sclerosis, we will conduct a series of ancillary studies that address potential biomarkers, changes in CNS pathology, aerobic fitness and metabolic effects on fat and muscle tissue as well as psychological factors that might influence treatment response and adherence.

To explore effects of exercise on MS-related gray and white matter pathology, we will obtain comprehensive MRI-based assessments of lesion load and pattern (double

inversion recovery (DIR), T2w, fluid-attenuated-inversion revovery (FLAIR), T1w), global and regional alterations of normal appearing gray and white matter (magnetization transfer (MTR), T2 prime (T2'), arterial spin labeling (ASL)), global and regional atrophy (e.g. brain parenchymal fraction, hippocampal subregional volumes, cortical thickness). Moreover, we will explore exercise effects on functional coupling during a cognitive task using task MEG (PASAT) and task fMRI (n-back with increasing complexity (2-back, 3-back, 4-back)).

Several myokines and cytokines have been hypothesized to mediate the beneficial effects of exercise on metabolic function as well as the CNS. We will use the opportunity of the AERCONN trial to study potential biomarkers such as brain-derived neurotrophic factor (BDNF) and the recently discovered myokine irisin in serum and plasma and investigate their association with clinical and imaging-based measures of brain function and integrity. New evidence from animal models suggests that the irisin pathway may be a key regulator involved in fat "browning" and other metabolic functions (Boström Nature 2012). Furthermore, irisin may directly induce "neuroprotective" molecules such as BDNF in the hippocampus (Wrann Cell Metab 2013) and could therefore be an interesting peripheral biomarker for CNS effects of exercise. Therefore, we will use bioimpedance measurements to monitor fat and muscle composition as well as our clinical and neuroimaging-based measures of brain structure and function to explore if these associations can also be seen in humans.

Lastly, we will obtain standardized questionnaires covering training motivation and maintenance at month 3 and month 6 to explore psychological factors that may facilitate or impede treatment adherence.

13 Participant timeline (see Figure 3): *Time schedule of enrolment, interventions (including any run-ins and washouts), assessments, and visits for participants. A schematic diagram is highly recommended.*

Interested patients will first be contacted by telephone to screen eligibility. Eligible patients will then be enrolled in the study and baseline assessment appointments will be scheduled. All outcome parameters will be assessed at month 0 (baseline) and month 3 (post intervention). *Each of these assessment blocks* includes 5 separate days of assessment (see Figure 3): *Day 1*: Visit to the MS outpatient center for neurological scoring, neuropsychology etc; *Day 2*: Visit to the Dept Neurophysiology for MEG. *Day 3* and Day 4: Visit to the Dept Neuroradiology for MRI. *Day 5*: Visit to the Dept Sports

Medicine for spiroergometry etc. During the entire assessment block (approx 7 days), the patients will wear the Actibelt® accelerometer. Randomization will be performed AFTER completion of day 5 in assessment block Wk 0.

Day 1 Assessment plan: During the clinical visit to the MS Center of the UKE, the following steps will be completed: Informed consent, blood sample (10 min), demographics

and EDSS (10 min), patient selfreport questionnaires (IDS-30SR, HAQUAMS, FSMC, MSWS-12, 30 min), neuropsychological testing battery (90 min), 9-HPT (5 min), 6MWT and T25 (10 min), MASC (20 min).

Day 2: MEG

assessments.

Day 3: Structural MRI assessments.

Day 4: Functional MRI assessments. Day 4 will only be done in 1/3 of the participants (i.e. the first 20 patients who

enter the trial).

(see inset).

Day 5 Assessment plan: The following assessments are conducted at the Dept Sports Medicine (in this order): Height and weight measurement (3 min), resting ECG (4 min), Bioelectrical Impedance Analysis (BIA, 6 min), spiroergometry (including blood draws before and after, 5ml plasma EDTA each, approx. 35 min), MFT-S3 assessment of balance and trunk stability (12 min), strength assessment (35 min), additional questionnaires (IPAQ (Lee 2011), Stadienzugehörigkeit im Transtheoretischen Modell (Basler 1999), Intention und Sportbezogene Selbstkonkordanz (Seelig & Fuchs 2006), Sportbezogene Konsequenzerwartung (Fuchs 1994), Sportbezogene Situative Barrieren und Management (Krämer & Fuchs 2010), sportbezogene sozialen Unterstützung (Fuchs 2008), Sportbezogene Selbstwirksamkeit (approx. 30 min)).

14 Sample size: Estimated number of participants needed to achieve study objectives and how it was determined, including clinical and statistical assumptions supporting any sample size calculations

Sample size was calculated based on results obtained in the pilot study on exercise and cognitive function in progressive MS (Briken et al., MSJ 2013). Below are the power calculations for the VLMT learning (trials 1 through 5) and delayed memory (trial 7).

14.1. VLMT Learning:

Numeric Results for Two-Sample T-Test

Null Hypothesis: Mean1=Mean2. Alternative Hypothesis: Mean1<>Mean2

The standard deviations were assumed to be unknown and equal.

Power	N1	N2	Ratio	Alpha	Beta	Mean1	Mean2	S1	S2
0.90388	20	20	1.000	0.02500	0.09612	4.0	9.8	5.0	5.0
0.81609	16	16	1.000	0.02500	0.18391	4.0	9.8	5.0	5.0
0.90639	17	17	1.000	0.05000	0.09361	4.0	9.8	5.0	5.0
0.80985	13	13	1.000	0.05000	0.19015	4.0	9.8	5.0	5.0

Group sample sizes of 20 and 20 achieve 90% power to detect a difference of -5.8 between the null hypothesis that both group means are 4.0 and the alternative hypothesis that the mean of group 2 is 9.8 with estimated group standard deviations of 5.0 and 5.0 and with a significance level (alpha) of 0.02500 using a two-sided two-sample t-test.

14.2. VLMT Delayed recall:

Numeric Results for Two-Sample T-Test

Null Hypothesis: Mean1=Mean2. Alternative Hypothesis: Mean1<>Mean2

The standard deviations were assumed to be unknown and equal.

Power	N1	N2	Ratio	Alpha	Beta	Mean1	Mean2	S1	S2
0.91886	17	17	1.000	0.02500	0.08114	0.6	3.2	2.0	2.0
0.81514	13	13	1.000	0.02500	0.18486	0.6	3.2	2.0	2.0
0.91148	14	14	1.000	0.05000	0.08852	0.6	3.2	2.0	2.0
0.82630	11	11	1.000	0.05000	0.17370	0.6	3.2	2.0	2.0

Group sample sizes of 17 and 17 achieve 92% power to detect a difference of -2.6 between the null hypothesis that both group means are 0.6 and the alternative hypothesis that the mean of group 2 is 3.2 with estimated group standard deviations of 2.0 and 2.0 and with a significance level (alpha) of 0.02500 using a two-sided two-sample t-test.

14.3. Summary statement:

Based on these calculations, powering for the dual primary endpoints VLMT learning and VLMT delayed recall, 90% power will be achieved with n=20 patients in each

arm of the trial. To safeguard against dropouts (based on previous experience, drop-out in behavioral trials often reach 20%) and the possibility that effect sizes in the pilot trial may have overestimated the real effect, we will enrol n=60 patients in the trial so that we will have approximately n=30 in each trial arm.

15 Recruitment: *Strategies for achieving adequate participant enrolment to reach target sample size.*

The Hamburg MS center has extensive expertise in patient recruitments for various behavioral and pharmacological therapeutic interventions in MS including 4 investigatorinitiated phase II drug trials, 2 phase I/IIa exercise studies, and several phase II behavioral intervention trials including RCTs of patient education programs and a CBT-based online intervention.

We will screen the registry database of the MS Day Hospital (n>7500) for patients who meet inclusion criteria (see below) and have indicated an interest in information about new clinical studies. These patients will be contacted by mail and invited to apply for participation in the trial. In addition advertisements for the study will be posted via the local self help society as well as the local MS network (www.ms-netz-hamburg.de).

Based on the recruitment in a previous exercise trial with more disabled patients and recent experiences within the NEUCONN-1 project, we expect to recruit and enroll 60 patients within 12 months.

16 Allocation

16a Sequence generation: Method of generating the allocation sequence (e.g., computergenerated random numbers), and list of any factors for stratification. To reduce predictability of a random sequence, details of any planned restriction (e.g., blocking) should be provided in a separate document that is unavailable to those who enrol participants or assign interventions.

Subjects will be randomized 1:1 to the exercise group or waitlist control using a computer-based random numbers generator. The randomization procedure does not include any stratification factors and no other restrictions (such as blocking).

16b Concealment mechanism: Mechanism of implementing the allocation sequence (e.g., central telephone; sequentially numbered, opaque, sealed envelopes), describing any steps to conceal the sequence until interventions are assigned.

A sequence of random numbers (1 or 2) will be generated by [name], placed in a sealed envelop, and stored a locked drawer in the office of the Dept Medical Biometry

and Epidemiology of the UKE. Every time a patient has completed day 5 of the Month 0 assessment (concealed allocation), [name] will call the secretary and obtain allocation for this subject. The entire random number sequence will never be accessible to any researcher involved in data acquisition, analysis, interpretation, and conductance of the AERCONN trial.

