Several studies have reported a positive association between aerobic fitness and cognitive parameters in healthy adults (Smith et al 2010; Etnier et al 2006). In addition, exercise interventions appear to enhance cognitive function in both healthy individuals as well as subjects at risk of dementia (Hillman et al 2006; Schulz et al 2012).

Work by Prakash et al (2010, 2011) provided first cross-sectional evidence for differences in gray matter density and resting state networks in trained versus untrained MS patients. Further supporting the biological rationale for CNS effects of exercise in MS,

evidence from the animal model of MS, experimental autoimmune encephalomyelitis (EAE), suggests that exercise might directly affect pathology as some studies indicate disease attenuation through exercise (LePage et al 1996) as well as axonal protection and enhancement of neuronal plasticity (Rossi et al 2009). However, to date for the effectiveness of exercise interventions on neuroprotection merely does not exist. To date, only one study has explored effects of low intensity level exercise on cognitive function in MS patients with minor disability (Oken et al 2006) showing no clear-cut effects. We have recently conducted a pilot trial with n=40 MS patients in the progressive phase (EDSS 4-6) comparing an 8 week (20 session) training period with hand- and bicycle ergometry as well as rowing to a non-exercising waitlist control group. We could demonstrate not only a significant beneficial effect on walking ability but also on neuropsychological tests of attention and verbal learning (Briken et al 2013). In this small trial now provides the basis for studying the effects of exercise on brain structure and function using neuropsychological tests as well as CNS connectivity in the current study. Novel imaging markers of CNS connectivity

MRI is regarded the most promising tool to assess tissue integrity in the brain in MS. However, due to the slow nature of neurodegenerative processes and the limited sensitivity of conventional MRI surrogate markers, predictive short-term changes have not been established (Barkhof et al 2009). Although non-conventional MRI markers such as T2 subtraction, brain atrophy, DTI or MTR as well as lesion evolution (Barkhof et al 2009; van den Elskamp et al 2010) might detect some aspects of neuroregeneration, until now they seem not sensitive enough for short-term changes.

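### Structural connectivity: the overall and motor fractional anisotropy values are assigned to cortex, where FA is a weak index of fibre connections

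*Protocol*

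**What the plan says.** Table 2 of the protocol (section 12.1) lists "Structural integrity and connectivity" among the secondary endpoints, with grey-matter density and DTI as the measures. Section 12.1.2 then defines the connectivity part: "Structural connectivity will be evaluated by measuring the fractional anisotropy (FA) calculated from Diffusion-Tensor Imaging data (DTI"). It goes on to fix the locations: "Overall cortical es well as regional (i.e. corpus callosum, primary and secondary motor cortex) FA values will be obtained". A second measure follows: "In addition, connectivity will be analyzed by probabilistic tractography focusing on the motor system", together with areas serving processing speed and working memory.

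The next paragraph of 12.1.2 turns to grey matter and names cortex as one of its regions: "Here, we will obtain overall and focal (cortex, hippocampus, thalamus) gray matter density measures".

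The protocol names no white-matter mask, skeleton or tract for the FA values. It gives no voxel size, signal-to-noise ratio or handling of partial volume for DTI.

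**The concern.** FA describes how strongly water diffusion is aligned in one direction. It is informative about connections where fibres run coherently, that is, in white matter. Cortex is a thin grey-matter ribbon between white matter and CSF. FA there is low, and the value in a voxel depends on noise and on how much of each tissue the voxel contains.

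Two things are at stake.

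- **Construct.** The only global FA summary and both motor summaries would be taken where the measure says least about fibre connections.
- **Attribution.** Section 6a cites cross-sectional differences in grey-matter density between trained and untrained patients. Section 12.1.2 makes cortical grey-matter density a secondary endpoint, and section 12.2 adds cortical thickness. If exercise alters cortical grey matter, the tissue mix in cortical voxels can shift in one arm and not in the other. The same change could then be reported twice, once as integrity and once as connectivity.

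Section 12.1.2 also plans to relate the functional connectivity results to the structural ones, so a poorly placed FA value would carry into those analyses. For MEG, the same section chooses measures that resist signal mixing. It states nothing comparable for DTI.

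**Working it through.** **No figure to reproduce.** The protocol gives no effect size, standard deviation or power for FA. Section 14 covers only the verbal learning test: "Below are the power calculations for the VLMT learning (trials 1 through 5) and delayed memory (trial 7"). The check is therefore a reading of the text plus an illustration.

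**Step 1: the FA summaries against the protocol's own tissue labels.**

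| FA summary (12.1.2) | Tissue, read literally |
|---|---|
| Overall cortical | Grey: cortex is a grey-matter region in the next paragraph |
| Corpus callosum | White |
| Primary motor cortex | Grey |
| Secondary motor cortex | Grey |

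Three of four are grey matter. The regional list is introduced by *i.e.*, so it reads as complete and not as examples.

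**Step 2: can noise and tissue mix matter at cortical FA levels?** For tensor eigenvalues λ1, λ2, λ3 with mean m, FA = sqrt[(3/2) × Σ(λi − m)² / Σλi²]. This cannot be negative, so noise pushes a true value near zero upwards.

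The simulation settings are all assumptions, because the protocol gives none: 30 directions, b = 1000 s/mm², one b0 image, Rician noise, log-linear tensor fit and 4,000 voxels per cell. White matter with FA 0.5 is mixed into the voxel along the same axis as the cortical tissue. Mean measured FA:

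| True cortical FA | SNR | No white matter | 10% | 20% | 30% |
|---|---|---|---|---|---|
| 0 | 15 | 0.142 | 0.150 | 0.173 | 0.206 |
| 0 | 25 | 0.084 | 0.098 | 0.133 | 0.175 |
| 0 | 40 | 0.052 | 0.073 | 0.115 | 0.163 |
| 0.10 | 15 | 0.168 | 0.196 | 0.227 | 0.262 |
| 0.10 | 40 | 0.112 | 0.150 | 0.190 | 0.231 |
| 0.20 | 15 | 0.240 | 0.264 | 0.292 | 0.319 |
| 0.20 | 40 | 0.205 | 0.236 | 0.268 | 0.298 |

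**Step 3: what the table shows.**

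- *Noise alone.* Tissue with no true anisotropy reads 0.05 to 0.14.
- *Tissue mix.* At true FA 0.10 and SNR 40, going from 10% to 20% white matter moves the reading by 0.190 − 0.150 = 0.040, with neither tissue's diffusion changed.
- *True signal remains.* At true FA 0.20, SNR 40 and no white matter, the reading is 0.205, almost the true value.

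**Limits.** CSF is left out. White-matter fibres running across the cortical axis would behave differently where true FA is above zero. The table shows that contamination can be large relative to a low FA. It does not show how large it would be here, or that the mix would shift within 3 months.

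**The case against.** The strongest objection is that *cortical* may be loose wording for cerebral, or for the white matter beneath the motor areas. A white-matter tract heads the regional list, which fits that reading, and masks are often settled in an imaging manual. The reading is possible. But nothing in the protocol points to a white-matter mask, and an analyst following the text would segment cortex. If white matter was meant, the text needs the same correction.

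A second objection is that section 20a compares change from Month 0 to Month 3 between randomised arms, adjusted for baseline. Noise and partial volume that are stable and common to both arms create no treatment difference; they cost sensitivity only. That stands. The false-attribution risk needs a differential change in cortical grey matter. The protocol treats that as plausible enough to test, and its density and thickness data would help to check it.

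A reader might also infer four stronger things, none of which the documents support.

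- *Cortical FA carries no information on fibres.* Without SNR, voxel size or region definitions this is too absolute, and the simulation retains true signal.
- *A null result would be silent on white-matter connectivity.* Callosal FA and tractography would still address it.
- *The background already concedes the point.* Section 6a says of several non-conventional MRI markers, DTI included, that "until now they seem not sensitive enough for short-term changes". That applies equally to white-matter FA, so it is no argument about location.
- *A percentage bias can be stated.* Any such figure would rest wholly on assumed tissue values and an assumed shift.

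**Conclusion.** The FA regions are badly fixed for their stated purpose. Taken literally, three of the four FA summaries, including the only overall one, are placed in tissue where FA is low and can be strongly affected by noise and partial volume. They are a weak index of structural connectivity, and an exercise effect on cortical grey matter could shift them without any tract change.

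The conclusion rests on the literal reading of *cortical* and on the general behaviour of FA in grey matter. The size of the distortion in this trial cannot be derived from the document.

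The reach is limited to these FA summaries within one secondary endpoint of an exploratory phase IIa trial. Verbal learning and memory, the sample size and the randomisation are not affected. It should be corrected before the imaging data are analysed by arm, but it does not threaten the main result.

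**What to change.** In section 12.1.2:

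- Replace the overall cortical value with mean FA over whole-brain white matter, for example over a white-matter skeleton.
- Replace FA in primary and secondary motor cortex with FA in the white matter or tracts connecting those areas, using the tractography already planned.
- Keep the corpus callosum.
- If cortical FA is still reported, label it exploratory grey-matter microstructure and state how partial volume is handled. Do not adjust it for grey-matter density measured after randomisation: exercise may itself change that density, so the adjustment could bias the treatment comparison.

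The cost is a change of region definitions in the image analysis. The same scans are used, with no new acquisition and no extra patients. If the change counts as one to an outcome measure, section 27 already sets the route: approval by the safety board, submission to the ethics committee and a note in the study registration.

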To determine the individual level of aerobic fitness, all patients will undergo a bicycle spiroergometry using the Metalyser 3b (CORTEX Biophysik GmbH, Leipzig, Germany). This test will be used as the anchor for the individualized training program (see below) as well as to monitor changes in aerobic fitness after the training intervention. The spiroergometry test starts with a resting-phase of 2 minutes. Ergometry will start at 25 Watts and performance will be continuously increased by 1 Watt every 4.8 seconds according to the WHO protocol (resulting in a ramp of 25 Watts/2min). We will continuously obtain stress ECG to monitor cardiovascular function (blood pressure (BP) and heart rate). Oxygen consumption will be recorded using the Metalyser 3b. In addition, blood draws for lactate assessment will be obtained with capillary pipettes (10µl) from one ear every 2 minutes and lactate values quantified by Biosen C-Line (EKF-diagnostic GmbH, Magdeburg, Germany). In addition, subjective exhaustion will be monitored by the Extended Borg scale (6-20) every 2 minutes. Patients will exercise under supervision until exhausted (Borg score of 18-20). Reasons for stopping (f.e. muscular fatigue, dyspnea) will be documented. For safety reasons, ergometry will also be stopped if a patient reaches systolic BP \ge 200 and/or diastolic BP \ge 110. If substantial ectopic electric heart activity or other complications occur, the spiroergometry will be stopped and the patient will be excluded from the study. After termination of the exhaustion test, spirometric data will be recorded for another 5 minutes. Lactate will be assessed after 1, 3, and 5 minutes during the cool-down period to detect the maximal lactate value. Two experienced exercise physiologists will determine the thresholds on the plots using semi-automated algorithms and blinded to patient identity. The Lactate thresholds AT and MaxLaSS will be determined using the first uptick in the lactate curve as well as the maximum change in lactate incline. Ventilatory thresholds 1 and 2 will be determined on the ventilation curve and confirmed by curves of ventilatory equivalents for O₂ (VE/VO₂), CO₂ (VE/VCO₂), and the slopes of VE and VCO₂, respectively (Wasserman et al., 1973). The maximum VO₂ value (ml \cdot kg⁻¹ \cdot min⁻¹) will be obtained close to exhaustion and will be considered as VO_{2peak}. The **anchor value** for the individually tailored exercise training will be the power (in Watts) recorded at Extended Borg scale score of 11.

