11 c: Strategies to improve adherence to intervention protocols, and any procedures for monitoring adherence (e.g., drug tablet return; laboratory tests).

We will obtain detailed information about each patient's time constraints and other commitments before inclusion to avoid drop-outs due to logistical difficulties. Particular attention will be given to potential problems with transfers to the study site and back. In addition, patients will be informed that symptoms might reappear or temporarily worsen during or soon after training sessions. Early telephone calls after 2-4 weeks of training will be used to detect barriers for adherence. During the last 2 weeks of training, a structured interview focusing on exercise motivation and barriers will be conducted with each participant. This interview will be repeated at month 6. Patients will also receive a summary feedback regarding their individual response to treatment with respect to physical fitness and clinical parameters.

11d: Relevant concomitant care and interventions that are permitted or prohibited during the trial.

In case of deterioration such as a relapse during the training program, the participant is requested to contact the study center and to discuss treatment option (e.g. steroid treatment) and / or training interruption. Steroid treatment of relapses and an interruption of the training of up to 2 weeks will be tolerated. Longer interruptions will be considered breach of protocol and the patient excluded from the per-protocol analysis (but retained in the intention-to-treat analysis).

12 Outcomes: Primary, secondary, and other outcomes, including the specific measurement variable (e.g., systolic blood pressure), analysis metric (e.g., change from baseline, final value, time to event), method of aggregation (e.g., median, proportion), and time point for each outcome. Explanation of the clinical relevance of chosen efficacy and harm outcomes is strongly recommended.

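### The MFT-S3 balance test is fixed straight after an exhaustive spiroergometry, so a Month 3 result on this tertiary endpoint cannot be separated from acute fatigue or recovery

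*Protocol*

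**What the plan says.** Section 13 of the protocol introduces the Day 5 list with "The following assessments are conducted at the Dept Sports Medicine (in this order". The sequence is height and weight, resting ECG, bioimpedance, spiroergometry, MFT-S3, strength assessment and questionnaires. The two items at issue read: "spiroergometry (including blood draws before and after, 5ml plasma EDTA each, approx. 35 min), MFT-S3 assessment of balance and trunk stability (12 min".

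Section 11a.1 describes the spiroergometry. Its target is exhaustion: "Patients will exercise under supervision until exhausted (Borg score of 18-20". Load rises on a ramp without a fixed end: "performance will be continuously increased by 1 Watt every 4.8 seconds according to the WHO protocol (resulting in a ramp of 25 Watts/2min". Some rides may end earlier on blood-pressure limits: "For safety reasons, ergometry will also be stopped if a patient reaches systolic BP". Afterwards, "After termination of the exhaustion test, spirometric data will be recorded for another 5 minutes", with lactate samples within that period. The same section says the test also serves to monitor the fitness change after training.

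Section 12.1.3 makes the MFT-S3 a tertiary endpoint: "we will objectively assess motor coordination and balance using the MFT-S3". Table 2 gives the construct as motor coordination and balance, with no reference to a post-exertion state. Section 20a analyses every outcome by ANCOVA on change from baseline, with the baseline of that outcome as the only covariate.

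**The concern.** Balance is tested on patients who have just cycled to exhaustion. The score therefore reflects both their balance and how tired they are, or how far they have recovered, when they step onto the device. That would matter less if the preceding exercise were a fixed dose. Here it is set by the patient's own capacity on a bicycle ergometer, and bicycle ergometry is also the intervention (section 11a). If training works as intended, the exercise arm arrives at the Month 3 balance test after a longer ride and more total work than the controls, but perhaps with faster recovery.

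At stake is how the MFT-S3 result can be read. A difference between arms could reflect better balance, a different acute load or quicker recovery. A null result could hide a balance gain offset by a harder ride. The analysis cannot undo this: ride time at Month 3 is measured after randomisation and is affected by treatment, so adjusting for it would not recover the effect on rested balance.

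**Working it through.** **1. Order and interval.** Setting section 13 beside section 11a.1, the events after the end of the ride and before the MFT-S3 are 5 minutes of recording and a blood draw of unstated length. No rest period or recovery criterion is given.

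**2. The ramp, as stated.** At 1 W every 4.8 s, 2 minutes give 120 / 4.8 = 25 W. This reproduces the protocol's 25 W per 2 minutes.

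**3. Ride time and work.** The ramp starts at 25 W.
- Ride time (s) = (peak W − 25) × 4.8
- Ramp work (J) = ride time × (25 + peak W) / 2

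The 240 W peak is the example patient in section 11a.2. The 150 W peak is an assumption, added to show a lower value.
- 240 W: 215 × 4.8 = 1,032 s = 17.2 min; work 1,032 × 132.5 = about 137 kJ
- 150 W: 125 × 4.8 = 600 s = 10.0 min; work 600 × 87.5 = 52.5 kJ

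**4. Effect of a fitness gain.** The documents give no expected gain in peak power, so a range is assumed.

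| Assumed gain | 240 W: extra time | 240 W: work ratio | 150 W: extra time | 150 W: work ratio |
|---|---|---|---|---|
| 5% | 58 s | 1.10 | 36 s | 1.11 |
| 10% | 115 s | 1.21 | 72 s | 1.22 |
| 20% | 230 s | 1.45 | 144 s | 1.45 |

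Worked line for 10% at 240 W: the new peak is 264 W; 239 × 4.8 = 1,147 s, which is 115 s more; work is 1,147 × 144.5 = about 166 kJ, and 166 / 137 = 1.21.

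**5. Does the 35-minute slot supply a standard rest?** Section 11a.1 adds 2 minutes of rest before the ride and 5 minutes of recording after it.
- 240 W: 35 − (2 + 17.2 + 5) = 10.8 min left for set-up and two blood draws
- 150 W: 35 − (2 + 10 + 5) = 18 min left

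How this remainder divides before and after the ride is not stated, and the slot length is approximate. The interval to the MFT-S3 may therefore exceed 5 minutes, but it is not controlled. If the slot were kept to, longer riders would have less time left in it.

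**6. Placement of the other motor test.** The six-minute walk test, also tertiary, is on Day 1, away from the spiroergometry. Of the motor performance tests in Table 2 that are done at a visit, only the MFT-S3 follows an exhaustive test. The strength assessment later on Day 5 has the same order problem but is not listed in Table 2.

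**The case against.** The strongest reply is that order and exhaustion target are identical in both arms and at baseline. The randomised comparison is then a fair one, and the baseline MFT-S3, taken under the same schedule, absorbs stable differences between patients in how readily they tire. The end of the ride is also defined by perceived exhaustion, so patients are meant to stop at the same subjective level whatever load they reach. All of this stands. It secures the comparison for balance after exertion; it does not make the score a measure of rested balance, which is how a reader would take Table 2.

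Several stronger readings are tempting and should not be drawn:

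- *That the MFT-S3 here measures fatigue and not balance.* It still measures balance and trunk stability, in a post-exertion state. Some rides may also stop on blood-pressure limits, so not every patient need be exhausted.
- *That trained patients do minutes of extra near-maximal work.* The whole ramp lengthens, mostly at lower relative load. Time above 90% of a patient's own peak is 0.1 × peak W × 4.8 s, so an assumed gain of 10 to 25 W adds only about 5 to 12 s there.
- *That the endpoint loses a known share of its effective sample.* The protocol gives no MFT-S3 variance, so no loss of precision can be computed.
- *That the order creates a fall risk.* The protocol neither describes the MFT-S3 procedure nor gives data on falls.
- *That the protocol itself concedes the point.* Its warning that "symptoms might reappear or temporarily worsen during or soon after training sessions" is advice about training, given under adherence in section 11c. It makes the concern plausible but says nothing about balance after spiroergometry.

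**Conclusion.** The point holds as a limit on interpretation, not as a flaw in the randomised comparison. The documents fix the MFT-S3 next after an exhaustive, open-ended ride and set no recovery criterion. The length of that ride depends on the fitness that the intervention is meant to change. A Month 3 difference on the MFT-S3, or its absence, therefore cannot be separated from arm-dependent acute fatigue or faster recovery.

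Neither the direction nor the size of any distortion of the score can be derived from the documents. The figures for extra ride time and work rest on assumed gains in peak power and describe the preceding exercise, not its effect on balance. The consequence is confined to one tertiary endpoint in an exploratory phase IIa trial. The primary VLMT belongs to the Day 1 neuropsychology and is unaffected. This is a cheap improvement worth making, and no main conclusion of the trial depends on it.

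**What to change.** In the Day 5 plan of section 13, move the MFT-S3 ahead of the spiroergometry: height and weight, resting ECG, bioimpedance, MFT-S3, spiroergometry, then the remaining items. Use the same order at every assessment block.

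The cost is the reordering of one 12-minute test within the same visit, with no added time, staff or procedure. The small downside is 12 minutes of presumably light standing work before the spiroergometry and its pre-test blood draw.

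If patients already have baseline MFT-S3 data under the present order, switching would make their baseline and Month 3 scores non-comparable. For them, keep the order, record ride time and the interval to the MFT-S3 for description only, and report the endpoint as balance after exertion.
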